The secondary estimand for fatigue severity will use the subpopulation of participants with HES aged 12 to 17 years. Treatment condition will be the same as for the primary estimand. A treatment policy strategy will be used for the intercurrent events of study treatment discontinuation and changes to background HES therapy. The endpoint will be the change from baseline in weekly average score of the BFI item 3 (worst level of fatigue during past 24 hours) for Week 52 and the summary measure will be the mean value.

Overall Design:

This is a 52-week, open-label, single arm, multicentre study of SC mepolizumab in children and adolescent participants with HES receiving SoC therapy.

Brief Summary:

The purpose of this study is to investigate the efficacy and safety of SC mepolizumab in paediatric participants aged 6 to 17 years with HES.

Approximately 15 participants who are on a stable dose of HES therapy for at least 4 weeks prior to Visit 2 will be enrolled. All eligible participants will receive mepolizumab, with the first dose administered at Visit 2, and subsequent doses administered every 4 weeks over a treatment period of 52 weeks (with a last dose at 48 weeks).

Concomitant SoC therapy may be adjusted as needed from 4 weeks after the first dose of mepolizumab. All participants will be managed during the study according to routine medical care.

All participants will attend a study-site visit at Screening (Visit 1), Baseline (Visit 2), Week 4 (Visit 3), Week 8 (Visit 4), Week 24 (Visit 8), and the Week 52 exit visit (Visit 15). The other study visits may be performed remotely where applicable country and local regulations allow. Home healthcare services may also be utilised to support these activities where local regulations and infrastructure allow. The final visit of the treatment period will be at Week 52. There is a follow-up visit at Week 60, 8 weeks after the Week 52 visit (12 weeks after the last dose of mepolizumab).

Eligible participants may enter an expanded access program (EAP), where available, immediately after completion of the 52-week study period. Participants who withdraw from the study prematurely will not be considered for an EAP.

Number of Participants:

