9. CCI [REDACTED]
[REDACTED]
10. When a CV flare is suspected during the study period based on investigator's judgement.
11. Only SAEs that are considered related to study procedures are to be collected from the time of signing informed consent.
12. Vital sign measurements will include temperature, systolic and diastolic blood pressure, and heart rate.
13. During the treatment period, all laboratory samples should be obtained pre-dose.
14. Eosinophil count samples for the screening visit only may be analysed by local labs if required. If a local sample is required, it is important that a sample for central analysis is obtained at the same time. Local lab eosinophil count results performed at the screening visit will be entered to the eCRF. If local lab samples are taken, a second sample will also be sent for central testing. The higher of the eosinophil cell count values is to be used to fulfil the entry criteria for enrolment.
15. Do not perform for each discontinuation visit, follow test frequency of Treatment Period schedule visit 2-15.
16. Negative urine pregnancy test result must be confirmed prior to dosing in female participants of reproductive potential. If a urine test cannot be confirmed as negative (e.g., an ambiguous result), a serum pregnancy test is required. In such cases, the participant must be excluded from participation if the serum pregnancy result is positive.
17. Pregnancy testing is only required until the end of systemic exposure, 12 weeks after the last dose.
18. Urine tests are done locally using dipstick. If found abnormal, the urine sample will be sent to the central laboratory for further testing.
19. If test was performed within 3 months prior to Visit 2, testing at Screening is not required. Test required are hepatitis B surface antigen and hepatitis C antibody. Participants with positive hepatitis C antibody due to prior resolved disease can be enrolled only if a confirmatory negative hepatitis C RNA test is obtained.
20. If no documented results are available.
21. For participants who discontinue treatment immunogenicity is to be performed 4 and 12 weeks after the last dose only.
22. For participants who discontinue treatment PK is to be performed 4 weeks after last dose only.
23. The date and time of the administration of study treatment will be recorded in the eCRF.

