6.8. Concomitant Therapy

Participants will be permitted to continue their SoC HES therapy (concomitant therapy) throughout the study period. Starting at 4 weeks after the first dose of mepolizumab (Visit 3), investigators may adjust SoC doses as medically appropriate based on clinical symptoms and blood eosinophil counts.

Any medication or vaccine (including over-the-counter or prescription medicines, vitamins, and/or herbal supplements) that the participant is receiving at the time of enrolment or receives during the study must be recorded, along with:

- reason for use
- dates of administration including start and end dates
- dosage information including dose and frequency

Any investigational agents (biologic or non-biologic) are not allowed within the 30 days or 5 drug half-lives, whichever is longer, prior to Screening (Visit 1), and until Visit 15. The term “investigational” applies to any drug not approved for sale in the country in which it is being used or investigational formulations of marketed products. Anti-IL-5 and anti-IL-5-receptor therapies are not permitted to be used during the study (from Visit 1 until the end of study visit, See Section 4.4), whether investigational or non-investigational.

For participants who are required to complete the follow-up visit, prohibited medications, such as anti-IL-5 / IL-5 receptor therapy, must not be started until the follow-up visit is complete. The follow-up period is required to reflect the safety information after 12 weeks from the last IP dose.

In general, GSK study participants can be vaccinated against COVID-19 using vaccines authorised via limited regulatory mechanisms (e.g., Emergency Use Authorisation [EUA]) or approved via accelerated or full approval mechanisms.

Use of other candidate COVID-19 vaccines that have not received limited, accelerated, or full authorisation/approval, and are only in use as part of a clinical trial, are not allowed.

The study Medical Monitor should be contacted if there are any questions regarding concomitant or prior therapy.

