8.2.5. Pregnancy Testing

Refer to Section 5.1 Inclusion Criteria for pregnancy testing entry criteria.

Pregnancy testing (urine or serum as required by local regulations) should be conducted prior to each dose of study intervention during study intervention period.

Pregnancy testing (urine or serum as required by local regulations) should be conducted at the end of relevant systemic exposure (at the follow-up visit).

Additional serum or urine pregnancy tests may be performed, as determined necessary by the investigator, or required by local regulation, to establish the absence of pregnancy at any time during the participant's participation in the study.

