8.3. Adverse Events, Serious Adverse Events, and Other Safety Reporting

The definitions of AEs or SAEs can be found in Section 10.3.

The definitions of device-related safety events, (adverse device effects [ADEs] and serious adverse device effects [SADEs]), can be found in Section 10.6. Device deficiencies are covered in Section 10.6.3.

AEs will be reported by the participant (or, when appropriate, by a caregiver, surrogate, or the participant's legally authorised representative).

The investigator and any qualified designees are responsible for detecting, documenting, and reporting events that meet the definition of an AE or SAE and remain responsible for following up AEs that are serious, considered related to the study intervention or the study, or that caused the participant to discontinue the study intervention (see Section 7).

The method of recording, evaluating, and assessing causality of AEs and SAEs and the procedures for completing and transmitting SAE reports are provided in Section 10.3.

8.3.1. Time Period and Frequency for Collecting Adverse Events and Serious Adverse Event Information

All SAEs will be collected from the start of study intervention until the follow-up visit at the time points specified in the SoA (Section 1.3). However, any SAEs assessed as related to study participation (e.g., study intervention, protocol-mandated procedures, invasive tests, or change in existing therapy) or related to a GSK product will be recorded from the time a participant consents to participate in the study.

All AEs will be collected from the start of intervention until the follow-up visit at the time points specified in the SoA (Section 1.3).

Medical occurrences that begin before the start of study intervention but after obtaining informed consent will be recorded as Medical History/Current Medical Conditions not as AEs.

All SAEs will be recorded and reported to the sponsor or designee immediately and under no circumstance should this exceed 24 hours, as indicated in Appendix 3. The investigator will submit any updated SAE data to the sponsor within 24 hours of it being available.

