4.8. Immunogenicity Analyses

4.8.1. Occurrence of anti-drug antibodies (ADA) and neutralising antibodies (NAb)

For the immunogenicity assessment, two types of anti-drug antibody (ADA) assays will be performed, a binding anti-drug antibody assay and a neutralizing antibody assay.

For the binding assay, there will be a three-tiered analysis: screening, confirmation and titration. The screening assay produces a result of positive or negative relative to a screening cut point. Positive samples continue with the confirmation assay, which also produces a result of positive or negative relative to a confirmation cut point. For positive confirmation samples, a titre value will also be obtained to quantify the degree of binding in a titration assay and the sample will be tested with the neutralizing assay, which also reports results as positive or negative.

The binding ADA results at each visit will be categorised as negative, transient positive (defined as a single confirmatory positive immunogenic response that does not occur at the final study assessment) or persistent positive (defined as a confirmatory positive immunogenic response for at least 2 consecutive assessments excluding the baseline visit, or a single result at the final study assessment). In addition, the highest post-baseline binding ADA confirmatory result obtained for a participant will be summarised. Participants with both positive and negative results will be identified in the positive category. Summary statistics for the titre result by visit will also be presented.

Neutralizing antibody assay results will be summarised by visit. In addition, the highest post-baseline neutralising antibody assay result during the treatment period of the study will be summarised, with participants with both positive and negative results identified in the positive category.

Furthermore, a summary of on-treatment adverse events (AEs) by highest post-baseline binding ADA confirmatory assay result [positive / negative] will also be generated.

Immunogenicity data will be listed for participants within the Full Analysis Set.

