6.2.2.3. Treatment Phases for Adverse Events

Study Phase	Definition
Pre-Treatment	AE onset date/time < Date/time of first dose of study treatment
On-Treatment	Date/time of first dose of study treatment ≤ AE onset date/time ≤ Date of last dose of study treatment + 28 days
Post-Treatment	AE onset date > Date of last dose of study treatment + 28 days

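### The AE-by-ADA table in SAP 4.8.1 stops counting AEs 28 days after the last dose but lets an ADA sample taken at 12 weeks set the child's status

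*SAP*

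**What the plan says.** **AE side.** SAP 6.2.2.3 defines on-treatment by the upper limit "AE onset date/time ≤ Date of last dose of study treatment + 28 days". Everything later is post-treatment ("AE onset date > Date of last dose of study treatment + 28 days"). AEs have no separate off-treatment phase, whereas flares do (SAP 6.2.2.1).

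**The table.** SAP 4.8.1 plans "a summary of on-treatment adverse events (AEs) by highest post-baseline binding ADA confirmatory assay result", split into positive and negative. No end date is set for the binding ADA result. The same section does limit the highest neutralising antibody result to the treatment period.

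**ADA sampling.** Protocol 1.3, Table 1 schedules immunogenicity at Weeks 0, 24 and 52 and at the follow-up visit. Footnote 21 has it taken 4 and 12 weeks after the last dose in children who stop treatment. Footnote 3 brings those children back for follow-up if the 12-week sample is missing.

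**Exposure and AE collection.** Footnote 17 of the same table states: "Pregnancy testing is only required until the end of systemic exposure, 12 weeks after the last dose". Protocol 8.2.5 places the end of exposure at the follow-up visit. Protocol 8.3.1 states: "All AEs will be collected from the start of intervention until the follow-up visit at the time points specified in the SoA". Protocol 6.8 adds: "The follow-up period is required to reflect the safety information after 12 weeks from the last IP dose".

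**Reporting.** Protocol 9.4.4 has on-treatment and post-treatment AEs summarised separately.

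**The concern.** A table of AEs by antibody status is meant to show whether antibody-positive children have different events. For that, the status and the events need to cover the same period. Here the status can be set by a sample at 12 weeks while the events stop at 4 weeks. The interval in which the antibody appeared is the one left out.

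A second gap concerns children who stop treatment early but stay in the study. Their post-treatment phase pools the eight weeks up to the protocol's stated end of exposure with all later time. No planned summary isolates AEs that began within the stated exposure period.

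**Working it through.** **1. The plan's own dates.** Last dose Week 48 + 12 = Week 60, and 60 − 52 = 8 weeks after the exit visit. This matches the Synopsis. The exposure formula in SAP 4.7.1 gives a completer 48 × 7 + 29 = 365 days. The on-treatment AE window, counted inclusively, is 48 × 7 + 28 + 1 = 365 days. The two agree, so the 28-day cut is consistent within the SAP.

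**2. The gap after the last dose.** 12 weeks = 84 days, and 84 − 28 = 56 days, which is 56/84 = 67% of the stated post-dose exposure. For a completer who attends Visit 16, observed time is 60 × 7 + 1 = 421 days, so the share is 56/421 = 13%.

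**3. Two children followed through the table (nominal visit dates).**
- *Completer.* ADA negative at Weeks 0, 24 and 52, first positive at Week 60. Status: positive. AEs counted: up to Week 48 + 4 = Week 52, the date of the last negative sample. AEs from Weeks 52 to 60 are excluded.
- *Last dose at Week 24.* ADA negative at Weeks 0, 24 and 28, positive at Week 36 (24 + 12). Status: positive. AEs counted: up to Week 28, again the date of the last negative sample. An AE at Week 33 falls 63 days after the last dose and is excluded.

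In both cases the positive column shows only events that began no later than the last negative sample.

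**4. What the post-treatment phase holds for early discontinuers followed to Week 52.** With last dose at week d, the phase lasts 52 − d − 4 weeks, of which 8 weeks are inside the 12-week period and 52 − d − 12 are beyond it.

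| Last dose (week) | Post-treatment (weeks) | Inside 12 weeks | Beyond |
|---|---|---|---|
| 0 | 48 | 8 | 40 |
| 12 | 36 | 8 | 28 |
| 24 | 24 | 8 | 16 |
| 36 | 12 | 8 | 4 |

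**5. Size for 15 completers.** The documents do not give the share p attending Visit 16 rather than entering the EAP. The time outside the window is 15 × p × 56/365.25 participant-years: 0, 0.57, 1.15, 1.72 and 2.30 for p = 0, 25, 50, 75 and 100%. On-treatment time is 15 × 365/365.25 = 15.0 participant-years. One child is 1/15 = 6.7 percentage points of an overall incidence.

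**6. Visit windows.** With Week 48 seven days early and Week 52 seven days late, the exit visit falls 28 + 14 = 42 days after the last dose. Up to 14 days before it then count as post-treatment.

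**The case against.** The case against has real weight.

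- **No event is lost.** AEs are collected to follow-up and shown as post-treatment. With about 15 children a reader can look at both tables. This stands, but those tables are not planned by ADA status and do not split discontinuers' time at 12 weeks.
- **28 days is a coherent convention.** It equals the dosing interval and matches the SAP 4.7.1 exposure formula and the flare phases. Protocol 8.2.4 also uses four weeks after the last dose for repeating abnormal laboratory tests. This stands, and it is why the main tables should keep the 28-day window.
- **Twelve weeks was not set for AE attribution.** Both exposure statements concern pregnancy testing, and 16 weeks is used for contraception and pregnancy collection. The legible text gives no half-life, so residual drug cannot be calculated. This stands as a limit. Even so, 12 weeks is the protocol's stated end of exposure and the time of the last planned ADA sample.
- **Late reactions look unlikely.** Protocol Table 2 describes systemic reactions within hours, sometimes days. It reports ADA in one participant (2%) at Week 32 of the placebo-controlled study. If 2% applied here (an assumption), 15 × 0.02 = 0.3 positives would be expected, with a 0.98^15 = 74% chance of none. The table may well be empty on the positive side. That lowers the stakes but does not make the definition right.
- **Limiting ADA to the treatment period might suffice.** If that period means 52 weeks, it removes the mismatch for completers on nominal dates. It does not do so for the child who stopped at Week 24, whose 12-week sample falls at Week 36.

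**Conclusion.** The AE and ADA sides of the table in SAP 4.8.1 have different horizons, and AEs from days 29 to 84 after the last dose cannot appear in it. Separately, no planned summary isolates AEs within the stated 12-week exposure period for early discontinuers. The effect is confined to descriptive safety reporting, and no hypothesis or estimand depends on it. Completers who enter the EAP without Visit 16 are unaffected on nominal dates. For them only the visit-window effect, at most 14 days, remains.

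A reader might go further and infer that the main AE, SAE and AESI tables understate events under exposure and should be rebuilt on an 84-day window. The documents do not support that. Days 29 to 84 are reported separately, and the AESI text (SAP 4.7.2.1 and 6.4.7) carries no on-treatment restriction. Moving the main tables would also separate them from the exposure formula and make observation length depend on EAP entry. Nor should the 67% be read as a share of events or of total exposure: it counts calendar days after the last dose.

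The conclusion rests on two assumptions. One is that the highest post-baseline result includes the 12-week sample. This is inferred from the unlimited wording and the sampling schedule, because the SAP does not say so directly. The other is that the protocol's 12-week statement is taken at face value.

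**What to change.** 1. In SAP 4.8.1, count AEs with onset from first dose to last dose + 84 days in the AE-by-ADA table, ending earlier at the first EAP dose or end of observation. State that the ADA status uses samples up to the nominal 12-week one, so both sides share one horizon. The ±7-day window can place that sample as late as day 91, so the SAP should say that it still counts.
2. Add one supplementary AE/SAE summary over the same period, so that events in early discontinuers within the stated exposure period can be seen apart from later ones.
3. Keep the 28-day on-treatment definition in SAP 6.2.2.3 for the main AE tables, consistent with SAP 4.7.1, and add a sentence giving its rationale.

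The cost is a short SAP edit and one or two extra tables, with slightly higher AE counts in them. No new data are needed, and protocol 9.4.4 sets no day limit that would have to change.

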6.2.2.4. Study Phases for Concomitant Medication

Study Phase	Definition
Prior	If medication end date is not missing and is before the date of first dose of study treatment
Concomitant	Any medication that is not a prior medication

6.2.3. Study Day and Reference Dates

The safety reference date is the study treatment start date and will be used to calculate study day for safety measures.

The efficacy reference date is the study treatment start date and will be used to calculate study day for efficacy measures and baseline characteristics, as well as efficacy durations.

The study day is calculated as below:

- Assessment Date = Missing → Study Day = Missing
- Assessment Date < Reference Date → Study Day = Assessment Date – Ref Date
- Assessment Date ≥ Reference Date → Study Day = Assessment Date – Ref Date + 1

6.2.4. Assessment Window

For summaries by visit, data recorded at an unscheduled visit will be re-assigned in the ADaM data sets to the closest nominal visit at which collection of data was scheduled, unless information already exists at that visit. Unscheduled data re-assigned to a scheduled visit will be included in analyses, summary tables and figures by scheduled visit. Unscheduled data that is not re-assigned to a scheduled visit will not be included in analyses, summary tables or figures by scheduled visit. Unscheduled data that is not re-assigned to a scheduled visit will be considered in the derivation of baseline and highest/worst case post baseline result for relevant summary tables.

Data recorded at the early withdrawal visit will be re-assigned in the ADaM data sets to the next scheduled visit, unless information already exists at that visit. Early withdrawal data re-assigned to a scheduled visit will be included in analyses, summary tables and figures by scheduled visit. Early withdrawal visit data that is not re-assigned to a scheduled visit will not be included in analyses, summary tables or figures by scheduled visit, but will be considered in the derivation of highest/worst case post baseline result for relevant summary tables.

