8.1.1. HES Flare

A HES flare is defined as a HES-related clinical manifestation based on a physician documented change in clinical signs or symptoms (worsening symptoms and/or elevated blood eosinophil level) resulting in the need for either of the following:

- An increase from the most recent dose in the maintenance OCS dose (prednisone/prednisolone equivalent) by at least 10 mg/day for 5 days
- An increase in or addition of any immunosuppressive and/or cytotoxic HES therapy from/to the most recent dose of HES therapy.

To be considered as a HES flare, the most recent dose of HES therapy must not have changed for at least 4 weeks prior to the flare. This ensures that failed reductions in HES therapy are not misclassified as a HES flare.

The start date for a HES flare will be defined as the date of therapy escalation confirmed by the investigator attributable to a HES-related clinical manifestation.

When a participant experiences a HES flare, the investigator will monitor the change in disease control per routine medical care (e.g., follow-up call) and record the resolution of the flare including the end date. Investigators are encouraged, as medically appropriate, to return the participant's treatment regimen to the level prior to the flare after the flare has resolved.

In the event of disease worsening for which the investigator suspects a HES flare between scheduled clinic visits, when possible, the participant will return to the clinic to have the unscheduled 'Flare' visit assessment completed as described in the SoA. When attending the clinic visit at the time of a suspected HES flare is not possible, the investigator should make every effort to evaluate the participant via telephone and complete the CCI [REDACTED]. If an escalation of therapy is initiated by a non-study physician, the investigator should confirm that the escalation in therapy is attributable to a HES-related clinical manifestation.

CCI

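### SAP 6.2.4 sets no maximum distance when it moves unscheduled readings into empty scheduled visits, so flare ECGs and vital signs taken months away can be reported as Week 24 or Week 52

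*SAP*

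**What the plan says.** SAP 6.2.4 has two re-assignment rules for by-visit summaries.

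- **Unscheduled visits.** A reading is "re-assigned in the ADaM data sets to the closest nominal visit at which collection of data was scheduled, unless information already exists" at that visit. The SAP adds: "Unscheduled data re-assigned to a scheduled visit will be included in analyses, summary tables and figures by scheduled visit". Readings that are not re-assigned stay out of by-visit displays but still count towards baseline and the worst post-baseline result.
- **Early withdrawal visit.** Its data go "to the next scheduled visit, unless information already exists at that visit". This sentence does not say whether the assessment must be scheduled at the target visit.

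Neither rule gives a limit in days or refers to treatment status. Both fill gaps only; neither replaces a value already present.

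The Flare visit falls under the first rule. Protocol 8.1.1 asks that participants, when possible, return to "have the unscheduled 'Flare' visit assessment completed as described in the SoA". In the Schedule of Activities (Protocol 1.3, Table 1), ECG is taken at Screening, Week 52 and Flare. Vital signs are taken at Screening, Weeks 0, 24 and 52, Flare and Withdrawal. The column for participants who discontinue treatment, headed as replacing Visits 2 to 15, contains neither. SAP 4.7.3.2 and 4.7.3.3 summarise change from baseline in vital signs and ECG by visit.

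**The concern.** A closest-visit rule is safe when visits are close together, because the spacing itself limits the shift. ECG and vital signs have very few scheduled post-baseline visits, so for them the spacing hardly limits it. The SAP sets explicit day windows for BFI item 3 and PROMIS (Table 3) and for medication (Table 4), but none for these safety measures.

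At stake is whether the Week 24 and Week 52 rows mean what their labels say. Change from baseline in ECG and in vital signs are listed safety endpoints, and Week 52 is the only scheduled post-baseline ECG. A reading taken during a suspected flare several months earlier, possibly off drug, would appear there as an end-of-treatment value. The rows are small. If everyone contributes, one such reading is 1 of 15 (about 7%). Safety is also shown by age group (SAP 4.9.1); at the minimum of 4 adolescents in the SAP version history, it is 1 of 4 (25%).

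**Working it through.** The documents state no figure for this point, so there is none to reproduce. The check asks how far the rule can move a reading.

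**Inputs.** Scheduled visits come from Protocol Table 1; the rule comes from SAP 6.2.4. Nominal weeks are used, before the ±7-day visit window.

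**Formula for unscheduled readings.** For neighbouring scheduled visits at weeks a and b, the nearest visit changes at (a + b)/2, so the largest shift is (b − a)/2.

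- **ECG** (Screening at Week −4 to −2, then Week 52). With Screening at Week −4, the midpoint is (−4 + 52)/2 = Week 24 and the largest shift is 28 weeks. With Screening at Week −2, the midpoint is (−2 + 52)/2 = Week 25 and the shift is 27 weeks. A flare ECG after that point is closest to Week 52. One before it is closest to Screening, which normally already holds a value.
- **Vital signs** (Weeks 0, 24, 52). The midpoints are (0 + 24)/2 = Week 12 and (24 + 52)/2 = Week 38. Week 24 can take a flare reading from 12 weeks before to 14 weeks after. Week 52 can take one up to 14 weeks early.
- **Chemistry** (Weeks 0, 12, 24, 36, 48). Largest shift 12/2 = 6 weeks.
- **Haematology** (every 4 weeks). Largest shift 4/2 = 2 weeks.
- **PK** (Weeks 4, 24, 52). No flare shift, because the Flare column has no PK sample.

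**Withdrawal readings.** There are two ways to read the next scheduled visit.

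- *Literal reading: the next 4-weekly visit.* The shift is under 4 weeks, or about 5 with the ±7-day window. A reading may land at a visit where that assessment is not scheduled.
- *Alternative reading: the next visit at which that assessment is scheduled.* Without a window, vital signs could move almost 24 weeks to Week 24 or almost 28 weeks to Week 52 (52 − 24). PK could move almost 20 weeks (24 − 4) or 28 weeks (52 − 24).

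**When the cell is empty.** The rule acts only then. That happens if the participant has left, missed the visit, or stopped treatment and is followed under the Discontinuation column, which has no ECG or vital signs. Such participants may still attend Flare visits, since Protocol 6.6 treats flare-related assessments as part of continued follow-up.

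**PK at withdrawal.** Footnote 22 to Table 1 says: "For participants who discontinue treatment PK is to be performed 4 weeks after last dose only". Its marker is on the Discontinuation column; the Withdrawal PK sample has no footnote. Suppose the last dose is at Week 8 and withdrawal at Week 22. The sample is then 22 − 8 = 14 weeks after the dose, and the literal rule files it under Week 24. Footnote 17 places the end of systemic exposure at 12 weeks after the last dose.

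**The case against.** **It may seldom operate.** Participants who stop drug are asked to stay to Visit 15 (Protocol 7.1), and all participants are to attend at Weeks 24 and 52 (Protocol 4.1). If the Visit 15 assessments still apply to them, the cell is filled and nothing moves. At the planning rate of 0.26 flares per year, 15 participants give about 0.26 × 15 = 3.9 protocol-defined flares in a year, though suspected flares may be more numerous. This stands as a limit on frequency. It does not settle the matter, because the Discontinuation column is headed as replacing those visits and omits both assessments.

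**Other rules may apply.** The ECG and vital-sign displays also follow the sponsor's core data standards, and SAP 4.6 on PK is redacted. Either could contain a restriction that a reader of these documents cannot see. This stands.

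**Stronger readings that the documents do not support.**

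- *Flare readings contaminate the PK summaries.* They cannot; no PK sample is scheduled at Flare visits.
- *Withdrawal readings move by months.* Read literally, they move about 4 to 5 weeks at most. The defect there is the undefined target visit.
- *Leavers' vital signs can come only from flares.* The Withdrawal visit also collects vital signs.
- *Off-drug PK samples shift the mean by a known percentage.* The dose groups and PK section are redacted, PK is excluded from the all-doses summary (SAP 4.1), and footnote 22 can be read as barring the late sample altogether.
- *The safety results are biased in a known direction.* Nothing in the documents fixes a direction.

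**Conclusion.** The point holds for ECG and vital signs. As written, SAP 6.2.4 can report a flare ECG as Week 52 when it was taken up to about 27 to 28 weeks earlier, and can move flare vital signs about 12 to 14 weeks into Week 24 or Week 52. This is more than missing detail: a stated rule can put a wrong visit label on a value in the change-from-baseline tables.

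The conclusion assumes that the scheduled cell is empty, that the flare was assessed in clinic, and that no unseen standard adds a limit. The consequence is confined to descriptive safety summaries; no hypothesis is tested. The flare-rate analysis and the OCS and BFI windows follow their own rules and are unaffected.

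Two smaller points remain: the next scheduled visit is undefined for withdrawal data, and it is unclear whether a withdrawal PK sample drawn long after the last dose may appear under a scheduled visit. The correction is cheap and worth making before database lock.

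**What to change.** In SAP 6.2.4:

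1. Re-assign an unscheduled reading only if it lies within a stated window of the target visit, for example the protocol's ±7 days. The exact width is for the sponsor to choose.
2. Show other Flare or unscheduled ECG and vital-sign readings in a separate row. Keep them in the worst-case post-baseline summaries, as the SAP already does for readings it does not re-assign.
3. For withdrawal data, define the next scheduled visit as the next one at which that assessment is scheduled, subject to the same window. The window is essential: without it, this definition allows shifts of up to about 28 weeks for vital signs and PK.
4. Unless SAP 4.6 already does so, do not summarise a withdrawal PK sample under a scheduled visit when it was drawn well after the dosing interval; list it by time since last dose. Reconcile footnote 22 with the unfootnoted Withdrawal PK sample.

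The cost is SAP wording and one programming condition. No reading is lost, but n falls in some by-visit rows. The loss is most visible for Week 52 ECG, where a participant without an ECG inside the window would no longer contribute.
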